4.11 DURATION OF THE STUDY

In general, the study will consist of 8 weeks of intervention plus 1 day of evaluations before and after the intervention. The window between the baseline appointment and the first day of the intervention can be from 1 to 30 days, and the window between the last day of intervention and the post intervention appointment will be from 8 to 38 days.

Assessment	Screening	Baseline Appointment	To be done at home	Intervention (8 weeks)	Post-Intervention Appointment
-------------------	-----------	----------------------	--------------------	----------------------------	-------------------------------

		(1 st day before Intervention)	(Pre &Post Intervention)		(1 st day after Intervention)
Assessment of eligibility criteria	X				
Written informed consent	X				
Demographic data, contact details	X				
Randomisation	X				
Weight		X			X
Height		X			
Blood Test		X			X
Blood Pressure		X			X
QMVCT		X			X
mMRC		X			X
CPET		X			X
CWRCT		X			X
Physical activity levels in daily life			X		
SGRQ (Questionnaire)			X		
HADS (Questionnaire)			X		
Intervention 1 st Group HIIT + HFNO				X	
Intervention 2 nd Group HIIT + NC				X	

Observation: There will be continual ECG monitoring during all the tests.

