1. INTRODUCTION

1.1 BACKGROUND

Interstitial lung disease (ILD) is a diverse group of entities that cause damage to the lung parenchyma through varying degrees of inflammation and fibrosis. Fibrotic ILDs result in restrictive ventilatory physiology and impaired gas exchange, frequently leading

to exertional hypoxemia and functional limitation (1). These diseases have been classified into various groups: ILD of known cause such as occupational or environmental exposures including Pneumoconiosis and Hypersensitivity Pneumonitis, ILD associated to connective tissue diseases/vasculitis, idiopathic interstitial pneumonias including idiopathic pulmonary fibrosis (IPF) and nonspecific interstitial pneumonia (NSIP), granulomatous ILD such as sarcoidosis and other rare forms of ILD including lymphangiomyomatosis (2, 3, 4). Among all these diseases the most common is IPF whose number of deaths in the UK according to the data from the office of national statistics increased from 1.66 per 100,000 people in 1979 to 8.29 per 100,000 people in 2016 (5). The mechanisms of reduced exercise capacity in ILD are multi-factorial. Impaired gas exchange occurs as a result of destruction of the pulmonary capillary bed and thickening of the alveolar-capillary membrane, resulting in ventilation-perfusion mismatch and oxygen diffusion limitations. Circulatory limitation results from pulmonary capillary destruction and pulmonary vasoconstriction and leads to pulmonary hypertension and cardiac dysfunction in some patients. Ventilatory limitations to exercise may also occur, although these are not thought to be a major contributor in most patients (6, 7). Peripheral muscle dysfunction is also a key factor to exercise limitation. Patients who suffer from ILD tend to avoid activities that trigger dyspnoea and fatigue, consequently they reduce their levels of physical activity, which leads to physical deconditioning and increasing symptoms. Furthermore, treatment with corticosteroids and immunosuppressants, as well as systemic inflammation, may also negatively impact on peripheral muscle function in some patients with ILD (6, 7). Pulmonary rehabilitation is an evidence-based, multidisciplinary and comprehensive intervention for patients with chronic respiratory disease who are symptomatic and often have decreased daily life activities. PR programmes include exercise training - which is the cornerstone of PR and includes aerobic conditioning, strength and endurance training respiratory therapy, education, nutritional interventions, psychological and social support and behaviour modification techniques (8, 9, 10). PR can be performed in different places; such as hospital outpatient departments, community health centres and even at home, showing similar results. PR has demonstrated improvements in symptoms, exercise tolerance and quality of life in chronic respiratory diseases other than COPD, including ILD and pulmonary hypertension, despite differences in underlying pathophysiology among them. Nevertheless, there is much less evidence of these improvements and the mechanisms by which pulmonary rehabilitation might improve outcomes in ILD compared to COPD (6, 7). Despite this, guidelines for pulmonary rehabilitation recommend its use in patients with chronic respiratory disorders other than COPD. Emerging evidence suggests that pulmonary rehabilitation may result in meaningful short-term benefits in patients with ILD, mainly on exercise tolerance, muscle function, dyspnoea and quality of life. However, the magnitude of these benefits is smaller than those generally seen in COPD and its ongoing effects are not evident six months after training (7). This may reflect the challenges in providing pulmonary rehabilitation for conditions such as idiopathic pulmonary fibrosis (IPF) that can be rapidly progressive (11). Guidelines for clinical management ILD point out that more information is needed on the benefits of pulmonary rehabilitation for this group of patients (7, 12). The greater prevalence of exercise-induced hypoxia, pulmonary hypertension and arrhythmia compared with other chronic lung diseases in this patient population raises the possibility that response to exercise rehabilitation may also differ (6, 7). In turn, high flow nasal oxygen allows the delivery of a well humidified high flow of air with a mix of oxygen from 21 to 100% and also provides a low level of positive end-expiratory pressure (PEEP). This strategy can achieve higher values of oxygenation even in acutely ill patients with ILD (13, 14) and may

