3 OUTCOME MEASURES

3.1 PRIMARY OUTCOME

The primary outcome will be Exercise Capacity, which will be assessed as endurance time (Tlim) during a constant work rate cycle test at 75% of the maximal workload (obtained beforehand from a maximal CPET).

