In addition, a Cardiopulmonary Exercise Test (CPET) will be carried out.

Furthermore, a Constant work rate Cycle Test at 75% of peak work rate (obtained from a maximal exercise test conducted beforehand) will be carried out. The participants will be able to rest for about 20 minutes between each test and we will offer them refreshments.

Physical activity levels in daily life will also be measured using Actigraph GT3x activity monitor, which will be delivered during the baseline appointment to use in their house for only 1 week before and 1 week after of the intervention, this is a belt that the participants will have to use like any other. After of the intervention they should return it to us during their post intervention appointment.

Moreover, two questionnaires called St George's Respiratory Questionnaire (SGRQ) and the Hospital Anxiety and Depression Scale (HADS), will have to be answered to measure the quality of life and anxiety and depression levels respectively. These test will be answered at home.

During the first day after of the intervention, participants will be undergone exactly to the same tests as in the baseline appointment, except height.

Intervention, a group of participants will be submitted to 8 weeks of a PR program based on HIIT plus HFNO and the other group will also be submitted to 8 weeks of a PR program based on HIIT but with conventional oxygen delivery without HFNO. Both HIIT will be performed at the same workload, which will be progressive throughout the 8 weeks and will be modified during each session. Starting with high load intervals at 60% of the maximal watts achieved beforehand during a maximal CPET divided by lower load intervals at 40% maximum load during the first week, and finishing with high load intervals at 110% maximum load separated by load intervals at 80% maximum load in the last weeks. Basically the participants will have to pedal in a stationary bicycle for 30 minutes (aerobic training), during the other 20 minutes the patients will do exercises for their upper limbs using Thera bands and dumbbells (strength training). Muscles of upper limbs to work will be deltoids, pectorals and biceps (3 series of 10 repetitions each). Finally the participants will receive 10 minutes of respiratory physiotherapy including techniques to eliminate phlegm, breathing exercises and ludic activities to train the respiratory muscles such as inflating balloons.

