5. DATA MANAGEMENT AND ANALYSIS

Data will be entered in an excel datasheet and imported to the statistical package SPSS version 23 for analysis. The anonymised database will be held in a university computer.

Physical activity level (PAL) data are handles in a standard manner: weekends are not being considered, only valid days (more than 8 h data) will be included in the analysis. At least valid data from two days need to be included as representative of valid PAL. Average of the days (minimum 2, max 5) will be the variable representing PAL. There will be different output of the monitor to include in the database (e.g. steps per day, energy consumption, etc.). Data from before the intervention and after the intervention will be generated in this manner and compared

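### The post-training visit that measures Tlim has two incompatible dates, and the 1-day minimum baseline gap cannot hold the required activity-monitor week

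*Protocol*

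**What the plan says.** The primary outcome (section 3.1) is "assessed as endurance time (Tlim) during a constant work rate cycle test at 75% of the maximal workload". After training, that test is done at the post-intervention appointment, which the protocol dates in two ways.

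- **As a window.** Section 4.11, and 4.1 in the same terms: "the window between the last day of intervention and the post intervention appointment will be from 8 to 38 days".
- **As a single day.** Section 4.1, later on: "During the first day after of the intervention, participants will be undergone exactly to the same tests as in the baseline appointment, except height". Section 4.7 also describes its test visits as taking place on the first day before and the first day after the intervention. In the schedule table of 4.11, the column that holds the constant work rate test is headed "1 st day after Intervention".

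For baseline, section 4.11 says: "The window between the baseline appointment and the first day of the intervention can be from 1 to 30 days". The activity monitor is given to the patient at the baseline appointment, for "use in their house for only 1 week before and 1 week after of the intervention", and is returned at the post-intervention appointment (4.1, 4.7). Section 5 leaves out weekends, counts a day as valid only with more than 8 hours of data, averages at most five days, and sets a floor: "At least valid data from two days need to be included as representative of valid PAL".

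**The concern.** Two questions arise.

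First, a site that follows the table would test patients the day after the last session, and a site that follows the text would test them between one and more than five weeks later. Different staff collect the data in Edinburgh and Newcastle (4.12.2), so the two sites could read the schedule differently. The background section says of rehabilitation in ILD that "its ongoing effects are not evident six months after training", so the time since the last session is not obviously irrelevant to Tlim. With about 30 patients and a plain t-test (section 6), avoidable variation in when the primary endpoint is measured is unwelcome.

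Second, a patient booked at the short end of the baseline window cannot wear the monitor for a week before training. Physical activity is a secondary outcome that compares before with after, so a patient without a valid baseline value drops out of that comparison.

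**Working it through.** The protocol states no figure of its own to reproduce here. The check is a day count.

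**Post-training visit**

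1. Permitted days under the window: 8, 9, …, 38, a spread of 38 − 8 = 30 days. Permitted day under the single-day wording: 1. The two sets do not overlap.
2. Full days between the last session and a visit d days later: d − 1. For d = 1 this is 0, and for d = 8 it is 7. The post-training wear week, with the device returned at this visit, therefore fits the window from its first day and cannot fit day 1.

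**Baseline visit**

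Let the baseline appointment be day 0 and the first session day d. The wear days available before training are d − 1 if only full days count, or d if the hand-out day also counts.

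3. A 7-day week needs d − 1 ≥ 7, so d ≥ 8. If the hand-out day counts, it needs d ≥ 7.
4. Of the 30 permitted gaps, 7 (1 to 7 days) are too short on the first count and 6 (1 to 6 days) on the second: 7/30 = 23% and 6/30 = 20%. These are shares of permitted gaps, not of patients. The protocol does not say how bookings will be spread.
5. Weekdays available, assuming that the appointment and the first session both fall on weekdays:

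| Gap (days) | Full weekdays between | Including the hand-out day |
|---|---|---|
| 1 | 0 | 1 |
| 2 | 1 | 2 |
| 3 | 0 (Friday to Monday) or 2 | 1 or 3 |
| 4 | 1 (Thursday to Monday, Friday to Tuesday) or 3 (Monday to Friday) | 2 or 4 |
| 5 | 2 | 3 |
| 6 | 3 | 4 |
| 7 | 4 | 5 |
| 8 | 5 | 6 |

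6. Against the two-valid-weekday floor in section 5:
   - A 1-day gap and a Friday-to-Monday gap fail however the hand-out day is counted.
   - A 2-day gap, and a 4-day gap that spans a weekend, reach two only if the hand-out day itself yields more than 8 hours of data.
   - The other 3 and 4 day gaps, and every gap of 5 days or more, offer at least two full weekdays.

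**The case against.** The best defence is that the first-day wording is only a label. Sections 4.1 and 4.11 describe one day of evaluations before and one after the intervention. The baseline column carries the matching first-day-before label although its window runs to 30 days. Only the windows are written as permitted intervals, and they appear twice. The monitor week and the return of the device at the post visit exclude day 1 in practice. Most of this stands, and it is why the window is the likelier intention. It does not remove the conflict: nowhere does the protocol say that the wording is a label, and section 4.1 uses it as an instruction for when the tests are done.

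A reader might go further and infer from the six-month remark in the background that a known share of the gain is lost by day 38. The document does not support that, because it gives no decay curve. A straight-line fall to zero at 182 days would give 38/182 = 20.9%. An exponential fall with rate 3/182 per day would give 1 − exp(−3 × 38/182) = 46.5%. The choice of curve sets the answer. Both figures also describe the total training gain, whereas the trial compares two arms that both receive HIIT at the same workload (4.10).

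A reader might also infer bias from open-label booking. Nothing in the protocol suggests that one arm would be seen later. A delay at one site would bias the comparison only if the arms were also unbalanced within sites.

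On the monitor, it is fair to say that this is a secondary outcome, that 23 or 24 of the 30 permitted gaps hold the full week, and that a truncated week is often still analysable under section 5.

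**Conclusion.** Both points hold, within limits.

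The protocol gives two dates for the primary endpoint that cannot both be met. The 8 to 38 day window is probably meant, but that is inferred from the monitor procedure and the protocol does not say it. The consequence is a risk of wrong or inconsistent test dates. No bias, added variance or detraining loss can be calculated from the document, and the 30-day spread of the window is not in itself an error.

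The baseline minimum is inconsistent with the monitor instruction whichever way the first conflict is resolved. Gaps of 1 to 6 days (1 to 7 if only full days count) shorten the week. Certain loss of the baseline value is confined to 1-day and Friday-to-Monday gaps. Loss is possible for 2-day gaps and for 4-day gaps across a weekend. It would be wrong to conclude that every patient who starts within a week of baseline lacks usable data. These counts assume weekday appointments and sessions, and no wear before the baseline visit.

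**What to change.** - **Post-training timing.** Correct the first-day-after wording in 4.1, 4.7 and the table header so that it agrees with the stated window, if the sponsor confirms that the window is intended. State that the same rule applies in both arms and at both sites. Record the number of days from the last session to the test. Narrowing the 30-day spread is optional: it would make timing more uniform but could put more visits out of window.
- **Baseline gap.** Raise the minimum from 1 to 8 days in 4.1 and 4.11, as on the post-training side, and keep the 30-day limit. An 8-day gap gives 7 full days and five full weekdays. The first-day-before wording in 4.7 and the table must then change too, because day 1 would no longer be permitted.

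The cost is an amendment to the wording and slightly tighter booking. Some patients would start training up to a week later than the present minimum allows.

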4.12 DATA COLLECTION

The UK General Data Protection Regulation (GDPR) requires appropriate technical and organisational measures to be in place to implement the data protection principles effectively and safeguard individual rights. This is ‘data protection by design and by default’.

In essence, this means we will integrate or ‘bake in’ data protection into our processing activities and business practices, from the design stage right through the lifecycle.

4.12.1 Data to be collected:

- Weight
- Height
- Blood Test (blood biomarkers associated with the progression of the fibrosis)
- Blood Pressure
- QMVCT (Strength of the Quadriceps muscle measured in Newtons)
- mMRC (score of dyspnoea from 1 to 5)
- CPET (Maximum workload measured in watts)
- CWRCT (time or exercise tolerance measured in minutes)
- Physical activity levels in daily life (measured in steps)
- SGRQ (Score of this questionnaire that measures the QoL)
- HADS (Score of this questionnaire that measures anxiety and depression levels)

4.12.2 Time points for collection: these data will be collected during the baseline and post intervention appointment by the CI ([name]) and the PI ([name]) in Edinburgh and by [name] (Physiotherapist) in Newcastle.

4.12.3 Details of standardised tools to be used:

- Modified version of the Medical Research Council scale (mMRC): see appendix D.
- Saint George Respiratory Questionnaire (SGRQ): see appendix E.
- Hospital Anxiety Depression Scale (HADS): see appendix F.

4.12.4 Methods to maximise completeness of data: PI will call participants who have not returned questionnaires.

4.12.5 How will data be recorded Data will be recorded using both eCRF and pCRF.

4.12.6 Source Data Documentation: Source data is defined as all information in original records and certified copies of original records or clinical findings, observations, or other activities in a clinical study necessary for the reconstruction and evaluation of the study. Source data are contained in source documents.

Source documents are original documents, data and records where source data are recorded for the first time.

We will use the medical records from Trak to obtain information of the high resolution computed tomography (HRCT) of the thorax, echocardiograms, breathing tests including Spirometry, Lung volumes and DLCO.

4.12.7 Case Report Forms: The case report forms (paper and electronic) will be entered in an anonymised database where patients will be with the study related unique study identifier number (ILDHIIT001....n) held in a university computer at Centre for Inflammation Research (CIR).

5. DATA MANAGEMENT AND ANALYSIS

Data will be entered in an excel datasheet and imported to the statistical package SPSS version 23 for analysis. The anonymised database will be held in a university computer.

Physical activity level (PAL) data are handles in a standard manner: weekends are not being considered, only valid days (more than 8 h data) will be included in the analysis. At least valid data from two days need to be included as representative of valid PAL. Average of the days (minimum 2, max 5) will be the variable representing PAL. There will be different output of the monitor to include in the database (e.g. steps per day, energy consumption, etc.). Data from before the intervention and after the intervention will be generated in this manner and compared

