3.2 SECONDARY OUTCOMES

Physical activity levels in daily life using Actigraph GT3x activity monitor, quadriceps muscle strength through the quadriceps maximal voluntary contraction test (QMVCT), quality of life using IPF-specific version of the St George's Respiratory Questionnaire (SGRQ), anxiety and depression levels through the Hospital Anxiety and Depression Scale (HADS), dyspnoea through the Modified version of the Medical Research Council scale (mMRC). The number of patients using anti-fibrotic medication will also be assessed.

Additionally, we will explore impact in blood biomarkers associated with fibrosis selected from the ELMEN study that have been shown to be associated with disease

progression (Inc. but not restricted to PAI-1, VEGF-A, PDGF-AA, PDGF-BB, Cystatin-C, Angioprotein-1, HE4/WFDC-2) (21).

We will also assess if the patients who are in treatment with antifibrotic medicines have better results than those who are not in treatment with antifibrotic medicines. This will be done in an exploratory way, where at the end of the study we will compare statistically if those patients who had a prescription of antifibrotics had better results compared to those who did not have a prescription of these medicines.

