4.10 INTERVENTION

The intervention consists of HIIT plus HFNO versus HIIT plus oxygen delivered through a nasal cannula. The oxygen delivered via HFNO will be between 31 and 37°C according to patient preference. To minimize condensation, the heated humidified gas is delivered via heated tubings through a wide-bore nasal prong. Air flow will be 50 L/min and FiO2 will be titrated to maintain SpO2 above 88%. The comparator will be oxygen delivered via nasal cannula titrated to the same SpO2. Both HIIT will be performed at the same workload, which will be progressive throughout the 8 weeks and will be modified during each session in order to achieve a Borg score of 5, starting with high load intervals at 60% of the maximal watts achieved beforehand during a maximal CPET divided by lower load intervals at 40% maximum load during the first week, and finishing with high load intervals at 110% maximum load separated by load intervals at 80% maximum load in the last weeks (see Appendix A and C).

Basically the participants will have to pedal in a stationary bicycle for 30 minutes, during the other 20 minutes the patients will do exercises for their upper limbs using Thera bands and dumbbells. Muscles of upper limbs to work will be deltoids, pectorals and biceps (3 series of 10 repetitions each). Finally the participants will receive 10 minutes of respiratory physiotherapy including techniques to eliminate phlegm, breathing exercises and ludic activities to train the respiratory muscles such as inflating balloons.

Which group will use HFNO or conventional oxygen will be randomly selected from a sealed envelope. Randomized means that all participants will have the same chance of belonging to one group or another, they must choose a sealed envelope and inside it will be written to which group they will belong.

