6. STATISTICS AND SAMPLE SIZE

We did not calculate the sample size, because this is a Randomized, Controlled, Multicentre Proof-of-Concept (PoC) study. However, we expect to recruit 30 ILD patients approximately.

Categorical variables will be summarized by frequency. Continuous variables will be expressed as mean \pm standard deviation (SD) or mean (95% confidence interval [CI]). For comparisons with the data for categorical variables or continuous variables between groups, a chi-squared test or Student's t-test will be used. The statistical analysis will be conducted with the program SPSS version 23. The level of significance for all comparisons will be set at $p < 0.05$. We will collect any adverse event information and it will only be collected on an ae log.

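### For physical activity, section 5 states only a before-versus-after comparison and leaves the monitor output open, which is not reconciled with steps in 4.12.1 or the between-group tests in section 6

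*Protocol*

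**What the plan says.** Section 3.2 lists the outcome by device, not by variable: "Physical activity levels in daily life using Actigraph GT3x activity monitor".

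Section 4.12.1 names one variable: "Physical activity levels in daily life (measured in steps").

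Section 5 builds the variable carefully: weekdays only, a minimum wear time per day, and an average over two to five valid days. It then opens the list of variables: "There will be different output of the monitor to include in the database (e.g. steps per day, energy consumption, etc".). It closes with the only analysis statement written specifically for this outcome: "Data from before the intervention and after the intervention will be generated in this manner and compared". No arm, contrast or test is given.

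Section 6 covers outcomes in general: "For comparisons with the data for categorical variables or continuous variables between groups, a chi-squared test or Student's t-test will be used". It has no paired test and no baseline adjustment, and it does not say whether the post-intervention value or the change is tested. One threshold applies throughout: "The level of significance for all comparisons will be set at" p < 0.05.

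Section 4.10 gives the randomised contrast, "The intervention consists of HIIT plus HFNO versus HIIT plus oxygen delivered through a nasal cannula", and states that "Both HIIT will be performed at the same workload".

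**The concern.** The trial asks what HFNO adds to HIIT. Both arms receive eight weeks of the same training, so any change in daily activity between the two monitor weeks contains the effect of training and the effect of time, whichever way oxygen is delivered. Only a comparison between arms removes that common part.

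The one sentence written for this outcome points to before against after. An analyst who followed it literally would run paired comparisons within each arm or over all patients. A rise that reaches significance in the HFNO arm and misses it in the nasal cannula arm could then be taken as a benefit of HFNO when the arms do not differ. With about 15 patients per arm, such a split is easily produced by chance.

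The open list of outputs is a second, smaller gap. Where one section says steps and another says steps, energy consumption and more, the choice of the variable that counts can be made after the data are seen.

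**Working it through.** **Side by side**

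| Item | Section 4.12.1 | Section 5 | Section 6 |
|---|---|---|---|
| Variable | Steps | Several outputs, list open | Not specific |
| Contrast | None given | Before versus after | Between groups |
| Test | None given | None given | Student's t or chi-squared, unadjusted |

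The protocol states no effect size, SD, power or error rate for physical activity, so there is no figure of its own to reproduce. The following is an illustration.

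**Inputs**
- Alpha 0.05 (section 6); two-sided is assumed, as sidedness is not stated.
- 15 per arm: assumed from about 30 patients in two groups. The 15 and 15 in section 4.2 are per site, not per arm.
- HFNO effect: zero, by assumption.
- Common true gain d in both arms, in SDs of the individual change: 0.3 and 0.5 assumed, with 0.8 as a further case.
- Complete monitor data and normal changes: assumed.

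**Before-after test in one arm (paired t-test, n = 15)**

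With 14 degrees of freedom, critical value t* = 2.145 and noncentrality d√n:

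P(p < 0.05) = 1 − F(t*; 14, d√15) + F(−t*; 14, d√15), where F is the noncentral t distribution.

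- d = 0.3: noncentrality 0.3 × 3.873 = 1.162, probability 0.192
- d = 0.5: noncentrality 0.5 × 3.873 = 1.936, probability 0.438
- d = 0.8: noncentrality 0.8 × 3.873 = 3.098, probability 0.821

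**HFNO arm significant, nasal cannula arm not**

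The arms are independent with the same probability P, so this is P(1 − P).

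**Between-arm t-test on change**

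Simulated, 100,000 trials per setting, 15 against 15.

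| Common gain d | HFNO arm p < 0.05 | HFNO arm only | Between-arm test on change |
|---|---|---|---|
| 0.3 | 0.192 | 0.192 × 0.808 = 0.155 | 0.049 |
| 0.5 | 0.438 | 0.438 × 0.562 = 0.246 | 0.049 |
| 0.8 | 0.821 | 0.821 × 0.179 = 0.147 | 0.051 |

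With 12 per arm the first column becomes 0.158 at d = 0.3 and 0.353 at d = 0.5, and the second 0.133 and 0.228. The picture does not depend on exactly 15.

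**Several outputs**

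This is a separate question, and it arises only if each output were tested between arms at 0.05. With no HFNO effect, the chance of at least one false positive from two independent outputs is 1 − 0.95² = 0.0975. By simulation it is 0.090 at correlation 0.5 and 0.076 at correlation 0.8. For three outputs the figures are 1 − 0.95³ = 0.143, then 0.124 and 0.099.

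**The case against.** A reader might infer that sections 5 and 6 contradict each other and that a before-after rise will be credited to HFNO. The protocol does not support either claim. Section 6 applies between-group tests to continuous variables and exempts no outcome. The closing sentence of section 5 follows a description of data processing, and it can be read as saying that both weeks are processed alike, after which the results go into the section 6 comparison. No statement says that a within-arm or pooled change will be taken as evidence for HFNO.

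A reader might also infer that every monitor output will be tested and the best one reported. Section 5 says only that the outputs go into the database.

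The 19% and 44% need care too. The calculation builds in a real gain, so rejecting no change is correct. These figures are power, and they become errors only if the result is read as an effect of HFNO.

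Finally, the choice of output and whether change or post-intervention value is tested are often left to a statistical analysis plan, and none is at hand.

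All of this limits the point but does not remove it. The complaint is not that detail is absent. The protocol does state a contrast for this outcome, and it is not the randomised one. It also describes the variable in two different ways. The harmless reading requires the reader to supply the arms, which section 5 does not mention.

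**Conclusion.** The point holds as an unreconciled ambiguity in the plan for a secondary outcome of a proof-of-concept study. As written, the comparison specific to physical activity cannot isolate HFNO, because both arms receive the same HIIT, and the variable that counts is not settled.

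If the before-after result were read as an HFNO effect, then with no such effect and an equal gain of 0.3 to 0.5 SD it would mislead in about 19% to 44% of trials on the HFNO arm's own test. On the pattern of significance in that arm alone, it would mislead in about 16% to 25%. A between-arm test on change keeps to about 5%. These sizes rest on the assumed gains, 15 per arm and complete data, and on a misreading that the protocol permits but does not announce. The analysis of endurance time is untouched.

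**What to change.** In section 5, replace the closing sentence with wording such as:

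> The physical activity outcome is mean steps per valid weekday. HFNO and nasal cannula are compared for the post-intervention week, with adjustment for the pre-intervention week by analysis of covariance. Other monitor outputs and within-arm changes are reported descriptively only.

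Add the same baseline-adjusted comparison to section 6. Otherwise its unadjusted t-test would disagree with the new section 5.

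A t-test on change between arms would also put the contrast right. ANCOVA is preferable: with equal SDs before and after and correlation ρ between the two weeks, the variance factors are 1 for the post-intervention value, 2(1 − ρ) for change and 1 − ρ² for ANCOVA. The last is never larger than the other two, since 2(1 − ρ) − (1 − ρ²) = (1 − ρ)². One degree of freedom is spent on the covariate.

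The cost is a few sentences of protocol wording. Both monitor weeks are already collected and steps are already listed in section 4.12.1. The sponsor gives up presenting other outputs or within-arm changes as tests of effect.
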